13.2 Sample Size, Accrual Rate and Study Duration

Accrual Targets				
Ethnic Category	Sex/Gender			
	Females		Males	Total
Hispanic or Latino	1+		2=	3
Not Hispanic or Latino	39+		66=	105
Ethnic Category: Total of all subjects	40+		68=	108
Racial Category				

American Indian or Alaskan Native	0+	0=	0
Asian	1+	2=	3
Black or African American	0+	0=	0
Native Hawaiian or other Pacific Islander	0+	0=	0
White	39+	66=	105
Racial Category: Total of all subjects	40+	68=	108

Sample Size. The total sample size for this investigation is between 6 and 108 patients, which includes 6 - 18 patients in the safety run-in, and up to 90 patients in the randomized portion.

Sample size estimates for the randomized trial are based on a proportional hazards mixture cure model with type-I error of 0.1, uniform accrual over 24 months, and 12 additional months of follow-up. The six-month global PFS proportion in the INP arm is assumed to be 0.6³ and follows an exponential distribution; it is also assumed that approximately 30% of patients in the INP arm and 50% of patients in the INT arm are cured (odds ratio = 2.33). Under these assumptions, there would be 80% power to detect a 6-month PFS rate of approximately 0.8 in the INT arm (hazard ratio = 0.557).⁴²

Accrual rate. Assuming accrual of about 3 patients per month across 6 sites and an equal allocation between experimental and control arms, 36 patients will be accrued within one year.

Study duration. Assuming unequal protocol activation times and holding accrual for analysis of safety run-in, study duration will be 4-5 years.

13.3 Stratification Factors

The randomization will be stratified by prior BRAF-directed therapy (yes/no) and prior therapy with anti-PD-1 treatments (yes/no).

13.4 Interim Monitoring Plan

Safety Run-in: The DLT observation period is 6 weeks. After all patients in a dose cohort have been followed for 6 weeks or had dose-limiting toxicity (DLT), enrollment will pause for review of the safety data. The safety reviews will decide whether to declare an MTD and proceed with the randomized trial, adjust the dose, or stop enrollment.

Early stopping rule for futility: An interim look for futility will take place when approximately 45 patients have been enrolled and treated on the Phase II portion of the trial (a total of 15 PFS events have occurred). A proportional hazards mixture cure model (Section 13.5) will be fit to the data at the time of the interim analysis and will be stratified by the randomization factors; randomized treatment will be the only predictor in this model. If the observed hazard ratio (INT vs. INP) from the latency portion of the model is 0.96 or larger then study enrollment will stop and the trial will cease due to futility.

Early stopping rule for neurotoxicity: Sequential boundaries will be used to monitor the rate of neurotoxicity (Section 7.3 Adverse Event Reporting) in the first 45 patients enrolled and treated in the Phase II portion of the trial. Accrual will be halted if excessive numbers of neurotoxicities are seen, that is, if the number of neurotoxicities is equal to or exceeds b_n out of n patients (see table). This is a Pocock-type stopping boundary that yields the probability of crossing the boundary = 0.1 when the rate of neurotoxicity is equal to 0.20.⁴³ Accrual will be halted if the number of neurotoxicities is equal to or exceeds b_n out of n patients, and the DSMB or DSMC may permanently stop the trial.

Table for neurotoxicity stopping rule:

Number of Patients, n	1	2	3	4	5	6	7	8	9	10	11	12	13	14	15	16	17	18	19	20	
Boundary, b_n	-	-	3	3	4	4	5	5	5	6	6	6	7	7	7	7	8	8	8	9	
Number of Patients, n	21	22	23	24	25	26	27	28	29	30	31	32	33	34	35	36	37	38	39	40	
Boundary, b_n	9	9	9	10	10	10	11	11	11	11	12	12	12	12	13	13	13	13	14	14	
Number of Patients, n	41	42	43	44	45																
Boundary, b_n	14	14	15	15	15																

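### The futility rule looks only at the latency hazard ratio of a mixture cure model at about 15 events, so it would stop the trial about 42–46% of the time when troriluzole works exactly as the sample size assumes

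*Combined protocol and SAP*

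**What the plan says.** Section 13.4 schedules one futility look, "when approximately 45 patients have been enrolled and treated on the Phase II portion of the trial (a total of 15 PFS events have occurred"). At that look the plan fits a mixture cure model of the proportional hazards type, stratified by the randomization factors, in which treatment is the sole covariate. The decision turns on the estimated INT-to-INP hazard ratio: if its value in the "latency portion of the model is 0.96 or larger then study enrollment will stop", which ends the trial. The wording is mandatory, and Section 5.11 has the Sponsor-Investigator follow the protocol-defined guidance. The cure (incidence) estimate does not enter the rule.

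Section 13.2 sets the design alternative in two parts. It assumes "approximately 30% of patients in the INP arm and 50% of patients in the INT arm are cured (odds ratio = 2.33"), together with a hazard ratio of 0.557, and says "there would be 80% power to detect a 6-month PFS rate of approximately 0.8 in the INT arm". Section 13.5 analyses both parts of the model at the end. Neither section gives the probability of stopping under the null or the alternative, or the power net of the futility look.

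**The concern.** The primary endpoint is global PFS, and the assumed gain comes partly from more cured patients and partly from slower progression among the uncured. A rule that reads only the second part ignores much of the gain.

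The second part is also poorly identified so early. At the look, median follow-up is about 6–7 months and, under the Section 13.2 curve, no plateau has formed. The likelihood can explain fewer INT events by more cure or by slower latency, and the data hardly distinguish the two.

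At stake is an irreversible decision. An effective regimen could be dropped almost as often as a useless one, and a benefit arising wholly through cure would be treated as no benefit at all.

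**Working it through.** **Inputs (Section 13.2 unless noted).** "type-I error of 0.1, uniform accrual over 24 months, and 12 additional months of follow-up"; up to 90 randomized, 1:1 (Section 13.1); control PFS at 6 months 0.6, exponential latency; cure 0.30 INP and 0.50 INT; latency hazard ratio 0.557. The look and the 0.96 threshold are from Section 13.4. No dropout is stated, so none is assumed.

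**Derived quantities.**
- Control latency hazard: −ln[(0.6 − 0.3)/0.7]/6 = 0.1412 per month.
- INT PFS at 6 months: 0.5 + 0.5·exp(−0.557 × 0.1412 × 6) = 0.812. A value of exactly 0.80 needs a hazard ratio of ln 0.6/ln(3/7) = 0.603.
- Accrual: 90/24 = 3.75 per month, so 45 patients at month 12. Expected events then are 8.2 (INP) + 4.0 (INT) = 12.1 under the alternative and 16.3 under the null. The two triggers in Section 13.4 therefore do not coincide.

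**The plan's own power figure.** For the log-rank test under local alternatives, the log-hazard difference at time t is δ(t) = β[1 + ln S₀(t)·π/S(t)] − γ·π/S(t). Here S₀ is latency survival, π = 0.3 the control cure fraction, S = π + (1 − π)S₀, β the log latency hazard ratio and γ = ln(7/3). Let D be the expected event proportion over 24 + 12 months (0.663) and I the integral of δ over the observed event density. Then N = 4(z₁₋α/₂ + z₀.₈)²·D/I².
- Hazard ratio 0.603, two-sided 0.1: I = −0.430, so N = 4 × (1.645 + 0.842)² × 0.663/0.430² = 88.7. Power at 90 is 80.5%, which reproduces the plan.
- Hazard ratio 0.557, two-sided: N = 80, power at 90 is 84%. One-sided alpha gives 89–91%.

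The design figure is sound before the futility look.

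**The futility rule.** Trials were simulated from these inputs. At the look, a semiparametric mixture cure model was fitted by EM, with treatment in both parts and baseline survival set to zero after the last event. This is the type of estimator named in Section 13.5. A large-sample check recovered a hazard ratio of 0.567 (true 0.557) and cure fractions 0.300/0.503 (true 0.30/0.50). The percentages are probabilities of stopping; ranges cover repeat runs of 500 to 4,000 trials, with 1,000 or more behind the first two latency figures.

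| Truth | Latency HR ≥ 0.96 (as written) | Cox PFS HR ≥ 0.96, unstratified |
|---|---|---|
| Design alternative, look at 15th event | about 42% (41–43%) | 4–9% over both looks |
| Design alternative, look at 45th enrolment | about 46% (45–46%) | as above |
| No effect | 51–54% | 50–56% |
| Cure benefit only (0.3 vs 0.5, HR 1) | 47–54% | 23–28% |

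With the truth at 0.557, the median estimated latency hazard ratio was between 0.76 and 0.90 across runs. In about 80% of the wrongly stopped trials the ordinary PFS hazard ratio was below 0.70 in favour of INT (median 0.42).

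**Sensitivity under the alternative.**
- Accrual of the first 45 over 15 months (3 per month): 41–44%.
- Hazard ratio 0.603: 41.5–46%.
- Reading 0.6 as PFS among the uncured: 44–52%.
- Progression dated at visits: 44–48%.
- Fully parametric exponential cure fit: 33–40%.
- Fits stratified as Section 13.4 asks, with assumed stratum shares: 40–45%. The Cox rule, stratified, stops 5–10%.

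**Effect on power.** A stopped trial cannot succeed, so power is at most 1 − 0.42 = 58% or 1 − 0.46 = 54%, whatever the final test. As an illustration with a two-sided log-rank final test, power falls from 84% to 45–50%; with the Cox futility rule it stays at 79–82%.

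**The case against.** The strongest counter-argument is that the size depends on inputs. At an assumed 2 patients per month, follow-up at the look is longer and the rule stops 34–36% under the alternative. Section 2.5 describes a historical control PFS of 61% at 6 months that loses only 5 points by 12 months and then stays flat, whereas the Section 13.2 inputs imply 0.3 + 0.7·exp(−1.69) = 43% at 12 months. With an assumed control curve of that flatter shape (cure 0.55, PFS6 0.61, same odds ratio and hazard ratio), the rule stops 25–32% at 15 events and 29–41% at 45 enrolled, against about 47–56% under the null. So it discriminates better there, though still poorly. These cases lie outside the plan's own design assumptions, and the false-stop rate remains large in all of them.

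Two further points stand in part. The 45–50% power figure uses a log-rank final test, while Section 13.5 bases inference on the cure model; the 54–58% ceiling does not depend on that choice. A Cox hazard ratio leaves the model family of Sections 13.2 and 13.5, hazards are not proportional under the mixture, and it would still stop about a quarter of cure-only benefits. Other remedies, such as a joint criterion on cure and latency or a later look, were not compared.

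The usual approximation does not rescue the rule. A standard error of 2/√15 = 0.516 gives z = (ln 0.96 − ln 0.557)/0.516 = 1.05 and a 15% false stop. That standard error belongs to an ordinary Cox hazard ratio and ignores the confounding of latency with cure.

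**Conclusion.** The rule is wrong as written. Under the Section 13.2 assumptions it stops an effective regimen about 42–46% of the time, only some 5 to 12 points less often than an ineffective one, and it does not separate a cure-only benefit from no effect. The 80% power in Section 13.2 cannot be attained if the rule is followed. The 42–46% rests on exponential latency, cure fractions 30%/50%, hazard ratio 0.557, accrual of 3.75 per month, no dropout and a semiparametric fit. Varying the estimator and the readings the plan leaves open gives 33–52%. Stratifying the fit does not change the conclusion.

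**What to change.** In Section 13.4, base the decision on the hazard ratio for global PFS from a Cox model stratified by the randomization factors, in place of the latency hazard ratio. Keep the 0.96 threshold. Keep the 15-event trigger and say that it governs, since 45 enrolments give only about 12 events under the alternative. State the stopping probabilities under the null, the design alternative and a cure-only benefit, and the power net of the look. If the sponsor prefers a joint criterion on cure and latency, the same operating characteristics should be shown for it.

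The cost is a short protocol amendment with the usual IRB approval across sites. The data and threshold stay the same, no patients are added, and the final cure-model analysis in Section 13.5 is unchanged. A futility-only look cannot inflate type I error; the change should be made before any unblinded interim result is seen.

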# If listed in protocol as expected and not requiring expedited reporting, event does not need to be reported.					
* For participants enrolled and actively participating in the study or for AEs occurring within 30 days of the last intervention, events must be reported within 1 business day of learning of the event.					
[∞] Additional Protocol-Specific Reporting for Select Neurotoxicities For this protocol only, select grade 2 neurologic toxicity lasting 4 days or more, with or without medical intervention (listed below) that are at least possibly related to study require expedited reporting within 5 calendar days 
 • Ataxia • Central nervous system necrosis (use this term for radiation necrosis) • Cognitive disturbance • Concentration impairment • Depressed level of consciousness • Dizziness • Encephalopathy • Guillain-Barre syndrome • Headache • Intracranial hemorrhage • Ischemia cerebrovascular • Leukoencephalopathy • Memory impairment • Presyncope • Reversible posterior leukoencephalopathy syndrome (PRES) • Stroke • Somnolence • Confusion (categorized under Psychiatric disorders) 					
Note: the select neurotoxicities above also meet the definition of a DLT in the Phase Ib portion.					

Protocol-Specific Adverse Event Reporting Exclusions

For this protocol only, the AEs/grades listed below do not require expedited reporting to the DF/HCC Sponsor-Investigator. However, they still must be recorded through the routine reporting mechanism (i.e. case report forms).

CTCAE System Organ Class	Adverse Event	Grade	Hospitalization/ Prolongation of Hospitalization	Attribution	Comments

Investigations	Laboratory abnormality	1-4	See comment	any	Laboratory abnormality without any clinical symptomatology (e.g. asymptomatic elevation of lipase). If the event results in hospitalization or prolongs hospitalization, the exclusion does not apply.

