12.2 Data Safety Monitoring

12.2.1 The DF/HCC Data and Safety Monitoring Board (DSMB) will review and monitor study progress, toxicity, safety and other data from the randomized portion of this study. The Board is chaired by a medical oncologist from outside of DF/HCC and its membership composed of internal and external institutional representation. Information that raises any questions about participant safety or protocol performance will be addressed by the Sponsor-Investigator, statistician and study team. Should any major concerns arise, the DSMB will offer recommendations regarding whether or not to suspend the study.

The DSMB will meet twice a year to review accrual, toxicity, response and reporting information. Information to be provided to the DSMB may include: participant accrual; treatment regimen information; all adverse events and serious adverse events reported across all sites by category; summary of any deaths on study; audit results; and a summary provided by the study team. Other information (e.g. scans, laboratory values) will be provided upon request.

12.2.2 The DF/HCC Data Safety Monitoring Committee (DSMC) will review and monitor study progress, toxicity, safety and other data from the safety run-in phase of this study. The DSMC meets monthly to review protocols and is chaired by a medical oncologist appointed by the Senior VP for Research. The DSMC will typically review a protocol every 3, 6, or 9 months based on protocol specifics. Information that raises any questions about participant safety or protocol performance will be addressed by the Sponsor-Investigator, statistician and study team. Should any major safety concerns or issues with data compliance arise, the DSMC will offer recommendations regarding whether or not to suspend the study.

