13. STATISTICAL CONSIDERATIONS

13.1 Study Design/Endpoints

It was recently shown that patients with small asymptomatic brain metastases can be treated with medical therapy rather than upfront radiation therapy.³ The response rate in this study was 48% and the intracranial and the extracranial response rates were largely concordant. Progression-free survival at 6 months (PFS6) was 61%. However, many patients progressed within the first 6 months. Therefore, freedom from progression at the 6-month mark is a clinically important and

measurable outcome.

We propose a multi-center, double-blind, randomized, phase II signal-detection trial with a non-randomized safety run-in to assess the efficacy and safety of adding troriluzole to ipilimumab/nivolumab induction and nivolumab maintenance in patients with melanoma that has metastasized to the brain. Patients will be randomly assigned in equal proportions to ipilimumab/nivolumab/placebo induction followed by nivolumab/placebo maintenance (INP) or ipilimumab/nivolumab/troriluzole induction followed by nivolumab/troriluzole maintenance (INT). The randomization will be stratified by prior BRAF-directed therapy (yes/no) and prior therapy with anti-PD-1 treatments (yes/no).

Safety Run-in: Up to three cohorts of patients will be treated in a 3+3 design with the triple drug combination to provide dosing information and an early assessment of safety. A starting dose of troriluzole at 140 mg/280 mg will be used; two fallback doses will also be investigated if the starting dose proves too toxic.

Cohort de-escalation table during safety run-in:

Dose Level	Troriluzole Dose
Starting cohort	140 mg PO QAM and 280 mg PO QPM
Cohort -1	140 mg PO BID
Cohort -2	140 mg PO daily
If ≥ 2 DLTs on Cohort -2	Permanently stop the trial

At the end of each cohort of the safety run-in, enrollment will pause for a comprehensive review of the safety data including dose-limiting toxicity (DLT). If fewer than two patients within a cohort have DLTs then that dose level will be considered the MTD and enrollment to the randomized trial will begin. If two or more patients within a safety cohort have DLTs, then the dose will either be de-escalated, or the trial will stop. A participant will be considered to have completed the DLT period with no dose limiting toxicities only if they have taken $\geq 80\%$ of their assigned Troriluzole doses in the DLT period, which is the first 6 weeks of treatment.

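### The neurotoxicity stopping boundary covers only the first 45 of up to 90 randomized patients; appending values to n = 90 is a cheap improvement that raises the chance of a halt at an assumed pooled 30% rate from 0.52 to 0.73

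*Combined protocol and SAP*

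**What the plan says.** Section 13.4 (Interim Monitoring Plan) sets a sequential boundary for neurotoxicity "in the first 45 patients enrolled and treated in the Phase II portion of the trial". Its table ends at n = 45, where the limit is 15 events. The action is stated: "Accrual will be halted if the number of neurotoxicities is equal to or exceeds b_n out of n patients". The DSMB or DSMC may then stop the trial permanently. The operating characteristic is also stated: "This is a Pocock-type stopping boundary that yields the probability of crossing the boundary = 0.1 when the rate of neurotoxicity is equal to 0.20". No crossing probability is given for any higher rate, and no reason is given for ending at 45.

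The event is defined by reference to Section 7.3, which lists "select grade 2 neurologic toxicity lasting 4 days or more, with or without medical intervention" and requires at least a possible relation to study treatment. The rule does not separate the arms, and Section 13.1 says "Patients will be randomly assigned in equal proportions".

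Section 13.2 provides for "up to 90 patients in the randomized portion". For the randomized portion, Section 12.2 adds general oversight: "The DSMB will meet twice a year to review accrual, toxicity, response and reporting information". It gives no numeric neurotoxicity threshold.

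**The concern.** Up to half of the randomized patients (90 − 45 = 45) would be enrolled with no numeric trigger for neurotoxicity. The protocol treats this risk as special. It names serious neurologic events in the secondary safety objective, makes select grade 2 neurotoxicities dose-limiting in the run-in, and gives neurotoxicity the only numeric toxicity boundary in the randomized part. Study drug runs to Day 337 and stereotactic brain radiation is allowed on study, so the risk does not end when patient 45 enters.

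The futility look in 13.4 also falls at about 45 patients, but it tests a PFS hazard ratio. Passing it says nothing about neurotoxicity. If the rule has only moderate power by patient 45, a raised rate that has not triggered it by then will meet no further numeric limit.

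**Working it through.** **Inputs.** The boundary values for n = 1 to 45, the reference rate 0.20 and the stated crossing probability 0.1 come from Section 13.4. The maximum of 90 comes from Section 13.2. The rates of 25%, 30% and 35% are assumptions, because the documents give no expected neurotoxicity rate and no target alternative. They are pooled rates: with 1:1 allocation, 30% could be 20% in one arm and 40% in the other, since (20 + 40)/2 = 30.

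**Method.** Let S(n, k) be the probability that the boundary has not been crossed after n patients and that k events have occurred. Then S(n, k) = (1 − p)·S(n−1, k) + p·S(n−1, k−1). All states with k ≥ b_n are removed and added to the crossing probability. This is exact and assumes that each outcome is known before the next check.

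**Step 1: reproduce the plan's figure.** The printed table at p = 0.20 gives 0.0978, which agrees with the stated 0.1. All 45 entries are also recovered as the smallest b with P(Bin(n, 0.20) ≥ b) ≤ 0.030. The table is correct for what it claims.

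**Step 2: performance of the current rule above 20%.** It crosses with probability 0.267 at 25%, 0.517 at 30% and 0.757 at 35%. At 30% it therefore fails to trigger with probability 1 − 0.517 = 0.483.

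**Step 3: values for n = 46 to 90.** The same construction, calibrated over 90 patients to an overall crossing probability of at most 0.10 at a 20% rate, uses a pointwise level of about 0.022. Its later values are:

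| n | 46–48 | 49–52 | 53–56 | 57–60 | 61–64 | 65–68 | 69–72 | 73–76 | 77–80 | 81–84 | 85–88 | 89–90 |
|---|---|---|---|---|---|---|---|---|---|---|---|---|
| b_n | 16 | 17 | 18 | 19 | 20 | 21 | 22 | 23 | 24 | 25 | 26 | 27 |

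**Step 4: compare the options.** "Appended" keeps the printed values for n = 1 to 45 and adds the row above. "Recalibrated" replaces the whole table with the 90-patient version.

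| True pooled rate | Current, n = 45 | Appended, n = 90 | Recalibrated, n = 90 |
|---|---|---|---|
| 20% | 0.098 | 0.118 | 0.099 |
| 25% | 0.267 | 0.378 | 0.354 |
| 30% | 0.517 | 0.727 | 0.714 |
| 35% | 0.757 | 0.936 | 0.932 |

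At 30%, appending catches (0.727 − 0.517)/0.483, or about 44%, of the cases that the current rule misses. At 35% it catches (0.936 − 0.757)/(1 − 0.757), or about 73–74%.

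**Step 5: sensitivity.** With the appended values at a 30% rate, the crossing probability is 0.60 if enrolment ends at 60 patients and 0.67 if it ends at 75. Recalibrating raises b_n by one at 12 of the first 45 looks (n = 4, 16, 19, 23, 26, 30, 34, 37, 38, 41, 42, 45), and detection by patient 45 at 30% then falls from 0.52 to 0.46. Continuing at the looser pointwise level of 0.03, instead of the values in step 3, gives 0.126 at 20% and 0.758 at 30%.

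**The case against.** The strongest reply is that nothing here is wrong. Section 13.4 says openly that the rule covers 45 patients, and the table delivers its stated property. Ending where the futility look falls is consistent with close early monitoring followed by general oversight, although the documents do not give that as the reason. This stands, and it is why the point is an improvement and not a correction.

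A reader might infer that a twice-yearly DSMB meeting is the only check after patient 45, with about 18 patients (3 per month × 6 months) entering unobserved between meetings. The documents do not support that. Section 7.3 requires related select grade 2 neurotoxicities to be reported within 5 calendar days, with its own time limits for other and higher-grade events, and does not confine this to the first 45 patients. Section 6.3 applies holding and dose-reduction rules to each patient throughout. Section 12.2 has the Sponsor-Investigator, statistician and study team address any safety question that arises. What is missing is a numeric trigger, not surveillance.

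A reader might also infer that detection can be raised to 0.71 at an unchanged 0.10 false-halt risk for nothing. That version needs a new table from n = 1 and weakens protection of the first 45 patients (0.52 to 0.46 at 30%).

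Two further limits stand. The rates are pooled, so crossing would not show that troriluzole is the cause; review by arm would be needed for that. And part of the gain comes late: at 30% the appended rule reaches 0.60 by patient 60 and 0.73 only by patient 90, when fewer patients remain to be spared.

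**Conclusion.** The numeric neurotoxicity limit covers at most half of the planned randomized enrolment, and at an assumed pooled 30% rate it has roughly even odds of triggering before it ends. Appending values to n = 90 raises the crossing probability by 0.11 at 25%, 0.21 at 30% and 0.18 at 35%, and leaves the first 45 looks unchanged.

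These sizes rest on three assumptions: the rates, which are not in the documents; full enrolment of 90; and outcomes known before each next check. With delayed outcomes or smaller enrolment the gain is less. If the trial stops for futility near 45 patients there is none.

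The point is a cheap improvement. It does not show an error in the stated rule, and it does not show that later patients are unmonitored.

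**What to change.** In Section 13.4:

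- State that the boundary applies to all randomized, treated patients, up to 90.
- Keep the printed values for n = 1 to 45 and append those for n = 46 to 90 (for example b46 = 16, b60 = 19, b75 = 23, b90 = 27; the full row is in the working).
- Restate the crossing probability at a 20% rate as about 0.12, and give the crossing probabilities at a few higher pooled rates.

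If the sponsor prefers to end at 45, the section should give the reason and report the rule's crossing probabilities above 20%.

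The cost is one sentence and one table block. The rule would count events of a kind that Section 7.3 already requires sites to report within 5 days. The statistical price is a false-halt probability of 0.118 instead of 0.098 at a 20% rate. A crossing halts accrual, and the DSMB or DSMC then decides whether to stop permanently, so a false crossing need not end the trial.
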